#### **8.5.4            *Pharmacokinetic Analyses***

Plasma concentrations of selpercatinib will be determined with a validated bioanalytical assay. The following PK parameters will be calculated from plasma concentrations determined on C1D8 if feasible:  $C_{max}$ ,  $T_{max}$ , area under the concentration versus time curve from time 0 to  $t$  ( $AUC_{0-t}$ ),  $AUC_{0-\infty}$ , apparent oral clearance ( $CL/F$ ), apparent volume of distribution ( $V_z/F$ ), and

$t_{1/2}$ . If appropriate, those PK parameters may also be calculated from plasma concentrations on C1D1, C3D1, and C5D1.

Summary statistics will be generated by dose cohort and across cohorts as appropriate.

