#### **6.3.2 Allowed Concomitant Medications**

Standard supportive medications may be used in accordance with institutional guidelines and Investigator discretion. These may include hematopoietic growth factors to treat neutropenia, anemia, or thrombocytopenia in accordance with American Society for Clinical Oncology guidelines (but not for prophylaxis in C1); RBC and platelet transfusions; anti-emetic, analgesic, and antidiarrheal medications; electrolyte repletion (e.g., calcium and magnesium) to correct low electrolyte levels; systemic glucocorticoids (approximately 10 mg per day prednisone or equivalent, unless there is a compelling clinical rationale for a higher dose articulated by the Investigator and approved by the Sponsor; no dose restriction for administration routes other than IV or oral), including short courses to treat asthma, chronic obstructive pulmonary disease, etc.; thyroid replacement therapy for hypothyroidism; and bisphosphonates, denosumab, and other medications for the treatment of osteoporosis, prevention of skeletal-related events from bone metastases, and/or hypoparathyroidism. Continuation of standard of care medications, including hormonal therapy for patients with prostate cancer (e.g., gonadotropin-releasing hormone [GnRH] or luteinizing hormone-releasing hormone [LHRH] agonists) and breast cancer (e.g., GnRH/LHRH agonists, aromatase inhibitors, selective estrogen receptor modulators [SERMs] or degraders [SERDs]), that the patient has been on for the previous 28 days, are allowed, provided they are not on the list of prohibited concomitant medications (refer to Section 6.3.3 and Appendix D).

Local treatment of tumor sites or target lesions while receiving selpercatinib (e.g., palliative radiation therapy or surgery for bone metastases) is permitted with Sponsor approval; however, the Sponsor recommends holding selpercatinib for approximately 5 half-lives (approximately 2-3 days) before and after radiation therapy or surgery. Any concern for disease flare due to a prolonged period off of selpercatinib should be discussed with the Sponsor, who may permit holding selpercatinib for a shorter period of time.

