Whole blood for genomic DNA	X											
Disease assessment v	X					Every 8 weeks (±7 days) starting with C3D1 through C13D1. Every 12 weeks (±7 days) thereafter.	Every 8 weeks (±7 days) through C13D1. Every 12 weeks (±7 days) thereafter.			X w		X
Confirmatory disease assessment y						At least 4 weeks post 1 st PR	At least 4 weeks post 1 st PR					

Visit Window	Screening	Cycle 1				Cycle 2-6	Cycle 7-higher b	Intra-patient Dose Escalation		EOT c	SFU d	LTFU e
	Day -28 to Day -1	D1 ±2 Days	D8 ±2 Days	D15 ±2 Days	D22 a ±2 Days	±3 Days	±7 Days	D1 ±3 Days	D8 ±3 Days			
Telemedicine Visit z							In parallel with local visits on non-disease assessment timepoints*					
Blood sample for PK aa			X						X			
EORTC QLQ-C30 or PedsQL bb		X				±7 days of each radiologic disease assessment	±7 days of each radiologic disease assessment			X		
Selpercatinib administration												
Patient dosing diary												
Patient bowel diary (MTC only) cc		X	X	X	X	D1 of C2-C6	D1 of C7, 8, 9, etc.*			X		
Adverse events dd												
Concomitant medications ee												
Survival ff												X

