### **7.8.3 Pharmacokinetics**

Plasma samples will be obtained for patients as outlined in Section 7. Additional PK assessments may be conducted in patients when considered necessary by the Investigator to understand exposure in relationship to possible safety or efficacy findings or if there is a change to the formulation of selpercatinib administered. Samples will be collected and handled as outlined in the Laboratory Manual, and concentrations of selpercatinib will be determined with a validated bioanalytical method. These data will be used to determine parameters such as  $AUC_{0-t}$  and plasma terminal elimination half-life ( $t_{1/2}$ ). The 0-8-hour duration of sample collection will be sufficient to cover a significant fraction of the area under the plasma concentration versus time curve.

Plasma samples will be obtained on C1D8 and D8 of a patient's new dose (if the patient is intra-patient dose escalated). PK parameters calculated from the drug concentrations in these samples will be used to compare the area under the concentration versus time curve from time 0 to infinity ( $AUC_{0-\infty}$ ) on D1 with the area under the concentration versus time curve calculated during the dosing interval at steady state ( $AUC_{\tau}$ ) and detect any auto-inhibition or auto-

induction of the PKs of selpercatinib (none is expected). Exploratory analyses to determine the presence and structures of metabolites of selpercatinib may also be conducted and the results of these analyses, if conducted, will be reported separately by the Sponsor.

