#### *Secondary Endpoints (Phase 1)*

- Frequency, severity, and relatedness of TEAEs and SAEs, changes in hematology and blood chemistry values, assessments of physical examinations, vital signs, and ECGs
- Plasma concentrations of selpercatinib and PK parameters, including but not limited to area under the concentration versus time curve from time 0 to 24 hours ( $AUC_{0-24}$ ),  $C_{max}$ , time to maximum plasma concentration ( $T_{max}$ ), and degree of accumulation
- ORR based on RECIST 1.1 or RANO, as appropriate to tumor type

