All deaths, including on-study deaths, that occur within 28 days of treatment discontinuation will be reported in a patient listing, which will include the primary cause of death and the number of days between the date of the last dose of study drug and death. For patients undergoing LTFU, the duration of survival following the initiation of study drug will be summarized in a descriptive manner using the Kaplan-Meier method. A summary of the anticancer therapies received after discontinuation of study drug will be provided.

Hematology and serum chemistries will be summarized in a descriptive manner by calculating the mean, standard deviation, median, and range, as follows:

- Baseline value
- Minimum post-baseline value

- Maximum post-baseline value
- Average post-baseline value
- Last post-baseline value.

Laboratory values will be assigned toxicity grades when available using the NCI CTCAE, version 4.03. Directional shifts in laboratory toxicity grades (comparing baseline grade with worst post-baseline grade) will be analyzed using standard shift tables, presenting number and proportion of patients and their maximum grade shift. For analytes without a toxicity grading scale, the shift table will present directional shifts from baseline to above or below the laboratory standard normal range using the maximum increase and/or decrease observed throughout the course of treatment/observation.

All patients will have pre-treatment baseline vital signs and pre-dose measurements on D1 of each cycle. The results for each vital sign will be summarized in a descriptive manner by calculating the mean, standard deviation, median, and range by time point in the same manner described for laboratory values. For these analyses, the minimum, maximum, average, and last post-baseline value will be determined relative to the baseline vital sign measurements only. In addition, serial vital signs measurements will be obtained pre- and post-dose on the first day of each patient's selpercatinib treatment in conjunction with serial PK sampling. For each patient, the vital signs change from the pre-dose value will be summarized in a descriptive manner. The Wilcoxon signed rank test may be used to assist in the identification of any systematic changes.

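### No scheduled sample supports the planned Day 1 PK comparison, and AUC(0-inf) taken from the Day 8 profile overstates dose/clearance about 1.7- to 2.3-fold under BID dosing

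*Protocol*

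**What the plan says.** **Sampling.** Section 7.8.3 states that "Plasma samples will be obtained on C1D8 and D8" of a new dose after intra-patient escalation. Table 7-1 marks PK blood in the same two places. Its footnote aa gives the times as pre-dose and 1, 2, 4 and 8 h. The Day 1 list in Section 7.2 and the list in Section 7.3 contain no PK draw.

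**Planned use of Day 1.** The same paragraph of Section 7.8.3 continues: "PK parameters calculated from the drug concentrations in these samples will be used to compare the area under the concentration versus time curve". The two areas compared are AUC(0-inf) on Day 1 and AUC(tau) at steady state, and the purpose is to detect auto-inhibition or auto-induction. The Phase 1 secondary endpoints in Section 8.1 end their PK item with "and degree of accumulation". Section 8.5.2 says that "serial vital signs measurements will be obtained pre- and post-dose on the first day" of treatment, alongside serial PK sampling.

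**Parameters.** Section 8.5.4 states: "The following PK parameters will be calculated from plasma concentrations determined on C1D8 if feasible". The list is Cmax, Tmax, AUC(0-t), AUC(0-inf), CL/F, Vz/F and half-life. If appropriate, "those PK parameters may also be calculated from plasma concentrations on C1D1, C3D1, and C5D1". No formula for CL/F is given. AUC(tau) is not in the list. Nor is AUC(0-24), although Section 8.1 (both phases) and SAP Section 1.1 name it as an endpoint. The SAP text provided has no section on PK analysis.

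**The concern.** There are two separate problems.

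1. The Day 1 comparison has no scheduled source. Day 8 samples cannot give a first-dose area, so neither an observed Day 8/Day 1 accumulation ratio nor the check for auto-induction or auto-inhibition can be produced from the schedule as it stands.

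2. AUC(0-inf) equals dose/clearance after a single dose. At steady state the corresponding quantity is AUC(tau). Extrapolating a steady-state profile to infinity adds the area from all earlier doses, so AUC(0-inf) from Day 8 is the wrong quantity as written.

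The two problems interact. If the Day 8 AUC(0-inf) were put in the Day 1 place, AUC(tau) would look like roughly half of it even with no change in clearance. That would read as auto-induction.

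At stake are descriptive secondary PK results and any exposure analysis that uses the affected parameters.

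**Working it through.** The documents give no numerical PK target, so there is no plan figure to reproduce.

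**Inputs**
- Half-life: Section 6.3.2 recommends holding drug for "approximately 5 half-lives (approximately 2-3 days) before and after radiation therapy or surgery". That implies 48/5 = 9.6 h to 72/5 = 14.4 h. It is an approximation, not a reported PK estimate.
- Dosing interval tau: 12 h for BID (Section 6.2.1); 24 h for the single QD level (Table 3-1).
- Sampling times: 0, 1, 2, 4 and 8 h (Table 7-1, footnote aa).
- Absorption rate ka: not in the documents; assumed 0.5, 1 and 2 per hour.
- Model: linear, one compartment.

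**Step 1: is Day 8 at steady state?** The fraction reached after 168 h is 1 − 2^(−168/t½). At the longest half-life, 14.4 h, this is 0.9997. Day 8 is at steady state.

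**Step 2: size of the AUC(0-inf) error.** With rapid absorption,

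R = AUC(0-inf) at steady state / AUC(tau) = 1 / (1 − 2^(−tau/t½)),

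and AUC(tau) = dose/CL. If CL/F is taken as dose/AUC(0-inf), it equals 1/R of its true value.

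| t½ (h) | R, BID | CL/F ÷ true, BID | R, QD | CL/F ÷ true, QD |
|---|---|---|---|---|
| 9.6 | 1.73 | 0.58 | 1.21 | 0.82 |
| 12 | 2.00 | 0.50 | 1.33 | 0.75 |
| 14.4 | 2.28 | 0.44 | 1.46 | 0.69 |

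At the protocol's sampling times, with the linear trapezoid, the true elimination rate and ka from 0.5 to 2 per hour, the BID ratios rise slightly: 1.74–1.82, 2.02–2.10 and 2.30–2.39.

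**Step 3: terminal slope estimated from the data.** In practice the slope must come from the samples. Fitting it to 2, 4 and 8 h under BID gives:
- ka 1 to 2 per hour: AUC(0-inf) inflated about 1.8- to 2.8-fold; estimated half-life 9.8–11.9, 12.3–15.0 and 14.8–18.2 h against true values of 9.6, 12 and 14.4 h;
- ka 0.5 per hour: AUC(0-inf) inflated 3.3- to 4.9-fold; estimated half-life 22.3, 28.8 and 35.4 h.

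The 8 h window is shorter than one half-life, which is why the slope is so poorly determined.

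**Step 4: what the 0–8 h window covers.** Section 7.8.3 says that the window captures a substantial share of the area. In the simulation it holds about 70–74% of AUC(tau) under BID, but only 24–41% of a single-dose AUC(0-inf). The statement is fair for the first quantity and not for the second.

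**Step 5: check of the alternative.** Using the pre-dose value as the end-of-interval point, the simulated AUC(tau) is 0.99–1.00 of true dose/CL for BID and 1.02–1.05 for QD. The Day 8 samples are therefore adequate for AUC(tau) and for CL/F derived from it.

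**The case against.** The strongest reply is that the plan leaves room.

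- Section 8.5.4 qualifies its list by feasibility and, where appropriate, allows concentrations from Day 1 of Cycles 1, 3 and 5.
- Section 7.8.3 allows extra PK assessments, and Section 8.5.2 presumes PK sampling on the first day.
- Accumulation is a Phase 1 endpoint only. Section 3.6.1 shows that escalation had already produced PK data, drawn from 89 patients, and the sampling schedules of earlier protocol versions cannot be seen.
- Section 8.5.4 does not say how CL/F is computed, and Section 7.8.3 names AUC(tau). With dose/AUC(tau), clearance would be nearly unbiased.

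Much of this stands, and it rules out some stronger readings. A reader might infer that Day 1 samples were never drawn and that accumulation cannot be estimated. The documents support only that such samples are not scheduled in the current version. Accumulation can also be predicted from half-life under linear PK, though 0–8 h data support that poorly. A reader might also infer that clearance will be wrong twofold. That follows only if CL/F is computed from the Day 8 AUC(0-inf). Nor is the Day 1 vital-sign summary invalid for want of PK blood: Section 8.5.2 only says that the two are taken together, and SAP Section 4.5.1 plans no such serial analysis.

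The reply does not remove the conflict. Section 7.8.3 derives its comparison from the Day 8 samples it has just described. None of the optional days in Section 8.5.4 is in the schedule. AUC(0-inf) is still listed for Cycle 1 Day 8, and a feasibility clause does not make it the right quantity at steady state.

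**Conclusion.** The point holds in this form. The current version schedules no sample that supports an observed Day 8/Day 1 accumulation ratio or the auto-induction and auto-inhibition check. AUC(0-inf) from the Cycle 1 Day 8 profile is wrong as written: it overstates dose/clearance about 1.7- to 2.3-fold for BID and 1.2- to 1.5-fold for QD, and more where absorption is slow and the slope is fitted to the 2–8 h samples. The first part needs no model. The size rests on linear one-compartment kinetics, a half-life derived from an approximate remark in Section 6.3.2 and, for the simulated figures, assumed absorption rates.

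CL/F and Vz/F are biased only if computed from that AUC(0-inf). Cmax, Tmax, AUC(0-t) and the primary ORR endpoint are unaffected. A reader might infer that the exposure-response objective is compromised, but Sections 2.5 and 8.1 do not name AUC(0-inf) or CL/F as the exposure measure.

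**What to change.** **In Section 8.5.4, for Cycle 1 Day 8**
- Replace AUC(0-inf) with AUC(tau). For BID this is AUC(0-12), with the pre-dose value used as the 12 h point.
- Add AUC(0-24) = 2 × AUC(0-12) for BID, to match the endpoint in Section 8.1 and SAP Section 1.1. For QD, AUC(tau) is AUC(0-24).
- Define CLss/F = dose/AUC(tau), with dose meaning the single administered dose.
- Do not report Vz/F and half-life from 0–8 h data, or flag them as unreliable.

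**Reconcile Sections 7.8.3, 8.1, 8.5.2 and 8.5.4 with Table 7-1**
- Restrict the Day 1 comparison and the observed accumulation ratio to patients who have Day 1 profiles, for example from earlier protocol versions, and state how many there are. Remove both if there are none.
- If those profiles also end at 8 h, say so. By Step 4, 59–76% of a Day 1 AUC(0-inf) would then be extrapolated.
- Correct the reference in Section 8.5.2 to PK sampling on the first day, and the unscheduled days named in Section 8.5.4.

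**Cost.** Changes to protocol and PK analysis wording; no new samples. Noncompartmental half-life and volume are no longer available as reliable estimates. Neither document describes a population PK model to supply them, so obtaining them that way would need a newly specified analysis.

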## **9. ADVERSE EVENTS**

An AE is any unfavorable medical occurrence in a patient administered an investigational product, which does not necessarily have a causal relationship with the treatment. Events meeting the AE definition include medication error, misuse, or abuse of IMP, including signs, symptoms, or clinical sequelae.

An AE can therefore be any unfavorable and unintended sign, symptom, or disease temporally associated with the use of the investigational product, whether or not considered related to the investigational product. All AEs that occur prior to the first dose are considered medical history unless the AE develops or worsens due to study related procedures. All SAEs, regardless of causality, that occurred from time of informed consent to SFU are to be recorded on the appropriate eCRF. Documentation must be supported by an entry in the patient's source medical records. Laboratory test abnormalities considered by the Investigator to be clinically relevant should be reported in the eCRF as an AE. Each AE is to be evaluated for duration, severity, and causal relationship with the investigational product or other factors. Serious AEs, including death, caused by disease progression should not be reported unless the investigator deems them to be possibly related to study treatment.

### **9.1 Safety Review Committee**

An SRC will be established to oversee the safety aspects of the Phase 1 portion of the study, and to render dose escalation decisions. Specifically, the SRC will perform ongoing review and adjudication of SAEs and other safety trends throughout the conduct of the study. The SRC membership will consist of the Sponsor's Medical Monitor, a Clinical Operations representative, and the Principal Investigator (or clinically qualified designee) from each active clinical site contributing patients to that cohort. The SRC will be convened for each cohort dose escalation decision or as needed. The SRC will only be required to convene prior to a cohort dose escalation if there is a DLT reported in a cohort. Decisions will be documented in written minutes.

The SRC established to oversee the safety aspects of the Phase 2 portion of the study will consist, at a minimum, of the Sponsor's Medical Monitor, a Clinical Operations representative, and the Global Principal Investigator. The Phase 2 safety committee will convene at a minimum of every 6 months for the first 5 years of the study, then annually (or more frequently depending on enrollment or observed safety profile) and perform ongoing review of SAEs and other safety-related data throughout the conduct of the study.

### **9.2 Grading and Intensity of Adverse Events**

The Investigator will grade the severity of each AE using, when applicable, the NCI CTCAE, version 4.03. In the event of an AE for which no grading scale exists, the Investigator will classify the AE as mild, moderate, severe, life-threatening, or fatal, as defined below.

- Mild (Grade 1) – An event that is usually transient in nature and generally not interfering with normal activities.
- Moderate (Grade 2) – An event that is sufficiently discomforting to interfere with normal activities.
- Severe (Grade 3) – An event that is incapacitating with inability to work or do usual activity or inability to work or perform normal daily activity.
- Life-threatening (Grade 4) – An event that puts the patient at immediate or potential risk of death.
- Fatal (Grade 5).

### **9.3 Relationship to Underlying Disease, Other Medical Condition or Concomitant Medications**

The Investigator will categorize each AE as to its potential relationship to underlying disease, other medical conditions or concomitant medications using the categories of Yes (causally related) and No (unrelated) as defined below. The assessment of the relationship of an AE to the underlying disease, other medical conditions, or concomitant medications is a clinical decision based on all available information at the time. In the absence of prior human data for this first-in-human study of selpercatinib, if the AE cannot be attributed to the patient's underlying disease, other medical conditions, or concomitant medication, and the temporal relationship of the occurrence of the AE with administration of the study drug suggests, then the AE will be assumed to be due to selpercatinib.

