**8.5.2 Safety Analyses**

Safety will be assessed by clinical review of all relevant parameters including AEs, SAEs, laboratory values, vital signs, ECG results, concomitant medications, and thyroid function.

Unless specified otherwise, the safety analyses will be conducted for the safety population defined in Section 8.2.1. The results of these analyses will be presented by tumor indication.

Summary tables and listings will be provided for all reported TEAEs, defined as AEs that start on or after the first administration of study drug. The reported AE term will be assigned standardized coding using MedDRA; the MedDRA version shall be specified in study documents, including but not limited to the coding plan and data management plan.

TEAEs will be summarized based on the number and percentage of patients experiencing the event by MedDRA System Organ Class and preferred term. The causal relationship between the occurrence of an AE and study drug will be judged by the Investigator based on the conventions described in Section 9.3. In the event a patient experiences repeat episodes of the same AE, then the event with the highest severity grade and strongest causal relationship to study drug will be used for purposes of incidence tabulations.

Tabular summaries will be provided for:

- All TEAEs.
- TEAEs by relationship (yes, no) to underlying disease, other medical conditions, or concomitant medications, and maximum severity grade.
- TEAEs with action of study drug delayed/interrupted or treatment reduced.
- TEAEs with action of study drug discontinued.
- All SAEs.
- SAEs by relationship (yes, no) to underlying disease, other medical conditions or concomitant medications.
- SAEs with action of study drug delayed/interrupted or treatment reduced.

The observed DLT rate in each dose cohort will be calculated by the crude proportion of patients who experience DLT. Multiple concurrent AEs leading to DLT will be considered a single DLT. The estimate of the DLT rate will be accompanied by a 2-sided 95% exact binomial CI.

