#### No:

The time course between the occurrence or worsening of the AE and underlying disease, other medical conditions, or concomitant medications rules out a causal relationship and another cause is suspected.

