#### Yes:

The time course between the occurrence or worsening of the AE and the underlying disease, other medical conditions, or concomitant medications is consistent with a causal relationship.

The following factors should also be considered:

- Temporal sequence from treatment with the study drug.
- Preclinical and prior clinical data regarding whether a particular AE could be an effect of the study drug (or class of drug).
- Pharmacology and PK of the investigational product.

An unexpected AE is an experience not previously reported or an AE that occurs with specificity, severity, or frequency that is not consistent with the current selpercatinib IB.

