### **9.4.1 Serious Adverse Event Reporting – Procedures for Investigators: Initial Report**

All SAEs occurring from the time informed consent is signed through 28 days after the last dose must be reported to Medpace Clinical Safety within 24 hours of the knowledge of the occurrence (this refers to any AE that meets any of the aforementioned serious criteria). All SAEs that the Investigator considers related to study drug occurring after the 28-day follow-up period must be reported to the Sponsor.

To report the SAE, complete the SAE form electronically in the EDC system for the study. When the form is completed, Medpace Safety personnel will be notified electronically and will retrieve the form. If the event meets serious criteria and it is not possible to access the internet, send an email to Medpace Safety at [[contact]](mailto:[contact]) or call the Medpace SAE hotline (phone number listed below), and fax the completed paper SAE form to Medpace (fax number listed below) within 24 hours of awareness. When the EDC system becomes available, the SAE information must be entered within 24 hours of the system becoming available.

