4.3.11.2. Adverse Events

Summary tables will be provided for all reported treatment-emergent AEs and treatment-emergent SAEs, defined respectively, as AEs and SAEs that started on or after the date of the first dose of selpercatinib (Study Day 1). For cases in which it is not possible to ascertain treatment-emergence, the event will be classified as treatment-emergent.

The reported AE term will be coded using version 21.0 of the MedDRA. The severity of each AE will be graded by the Investigator based on version 4.03 of the National Cancer Institute CTCAE. If a severity grading scale does not exist for an AE, the investigator will classify the severity as mild, moderate, severe, life-threatening/debilitating, or fatal based on the criteria described in study protocol. The causal relationship between the occurrence of an AE and study drug will be judged by the Investigator as "related" or "not related."

AEs will be summarized based on the number and percentage of patients experiencing events by MedDRA system organ class and preferred term. If a patient experiences repeated episodes of the same AE (as defined by the MedDRA system organ class and preferred term), the event with the highest reported severity grade and the strongest causal relationship to study drug will be used for purposes of the incidence tabulations.

Tabular summaries will be provided for treatment-emergent AEs and SAEs:

- all AEs
- by maximum severity grade
- by relationship to study drug
- AEs with action of study drug withheld or dosage modified

- AEs with action of study drug permanently discontinued
- SAEs

Narratives will be prepared for all patients who meet one or more of the following conditions:

- death while on treatment or within 28 days of the last dose irrespective of cause
- treatment-emergent SAEs
- AE with action taken of study drug permanently discontinued

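### Protocol 9.3 asks whether an AE is due to causes other than selpercatinib, the SAP tabulates relatedness to selpercatinib, and no rule covers an AE that fits both

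*Protocol*

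**What the plan says.** **Protocol Section 9.3** puts a Yes/No question to the investigator about causes other than the study drug: "The Investigator will categorize each AE as to its potential relationship to underlying disease, other medical conditions or concomitant medications".

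- Yes applies when the time course of the AE against underlying disease, other conditions or "concomitant medications is consistent with a causal relationship".
- No applies when that time course "rules out a causal relationship and another cause is suspected".
- A default follows: "if the AE cannot be attributed to the patient's underlying disease, other medical conditions, or concomitant medication", and the timing against study drug fits, the AE is assumed to be due to selpercatinib.
- The section also lists drug-side factors to consider (timing from study drug, preclinical and prior clinical data, pharmacology and PK). It does not say how they change the answer.

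**Protocol Section 8.5.2** adopts this as the standard for drug causality. The relationship between an AE and "study drug will be judged by the Investigator based on the conventions described in Section 9.3". It counts repeat episodes of an AE by the strongest causal relationship to study drug. Yet its two relatedness tables, one for TEAEs and one for SAEs, are by relationship to disease, other conditions or concomitant medications. No table by relationship to selpercatinib is listed.

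**SAP Section 4.3.11.2** has the investigator judge each AE as related or not related to study drug, and tabulates TEAEs and SAEs "by relationship to study drug". SAP Section 4.7, on changes to protocol-planned analyses, lists one change only: efficacy by indication instead of by cohort.

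**Protocol Section 8.1** names "Frequency, severity, and relatedness of TEAEs and SAEs" among the secondary endpoints of both phases.

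**The concern.** Relatedness is a named secondary endpoint, but the two documents measure it with different questions. Whether another cause is possible is not the complement of whether selpercatinib is possible, because one event can have both.

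Such events are foreseeable here. Protocol Section 6.2.4 says prior immune checkpoint inhibitors may contribute to liver function abnormalities. Section 6.3.3 and Appendix J anticipate co-medication that prolongs QTc. Liver enzyme increases and QT prolongation are also listed in Section 1.7.1 as AEs of special interest for selpercatinib. For these AEs the coding rule matters most, and it is missing.

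At stake are the drug-related AE and SAE rates in the study report. One reporting duty may also be touched. Section 9.4.1 says: "All SAEs that the Investigator considers related to study drug occurring after the 28-day follow-up period must be reported to the Sponsor". If an investigator uses the Section 9.3 convention to form that view, a late SAE with a competing cause could go unreported.

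**Working it through.** The protocol states no figure to reproduce on this point. The check has two parts: how the rule classifies an AE, and how large the effect could be.

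**1. Classification under each document**

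| AE fits | Section 9.3 answer | Column in Section 8.5.2 table | SAP 4.3.11.2 category |
|---|---|---|---|
| (a) selpercatinib only; other cause ruled out | No | No | related (by the default) |
| (b) other cause only | Yes | Yes | not related |
| (c) both | Yes (a compatible time course is enough) | Yes | not determined |

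The thresholds are not symmetric: compatibility is enough for Yes, while No needs exclusion. Group (c) therefore falls under Yes, and the default towards selpercatinib is not triggered.

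The Section 8.5.2 table puts (b) and (c) in the same column, so it cannot show how many events had selpercatinib as a plausible cause. The SAP's related count is (a) plus whatever part of (c) the investigators chose to call related. No text fixes that part. If the Section 9.3 answer were simply reversed to obtain drug relatedness, all of (c) would be counted as not related.

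**2. Ceiling on the size**

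Inputs: all-cause and related percentages from protocol Section 1.7.1 (cut-off 8 May 2022), and 825 treated patients from Section 1.7 at the same date. Section 1.7.1 does not restate its denominator, so 825 is an assumption for the patient counts.

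Gap = total % − related %. Patients = 825 × gap / 100. Share not called related = gap / total.

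| AE | Total % | Related % | Gap (points) | Patients | Share not called related |
|---|---|---|---|---|---|
| Hypertension | 41.5 | 28.7 | 12.8 | about 106 | 31% |
| Dry mouth | 48.7 | 38.4 | 10.3 | about 85 | 21% |
| AST increased | 37.8 | 28.8 | 9.0 | about 74 | 24% |
| ALT increased | 36.2 | 29.1 | 7.1 | about 59 | 20% |
| QT prolonged | 20.5 | 16.1 | 4.4 | about 36 | 21% |

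Each gap holds every patient whose event was not called related, including events correctly judged unrelated. The number in group (c) that were coded away from the drug is therefore at least zero and at most the gap. The documents give nothing that narrows this range.

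**The case against.** The strongest reply is that this is a wording mismatch and that drug relatedness is already assessed directly.

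- Section 9 requires each AE to be evaluated for causal relationship with the investigational product or other factors.
- The SUSAR definition in the protocol's list of abbreviations uses a reasonable possibility of a causal relationship with the study intervention. Section 9.4.1 adds that the sponsor confirms relatedness.
- Section 1.7.1 reports related percentages that are 69% to 80% of the all-cause rates, and Section 6.2.4 says investigators judged dry mouth related to selpercatinib in 37% of patients. Some direct judgement is being recorded.
- The default in Section 9.3 is a sufficient condition for blaming the drug. It does not say that an AE with another possible cause is unrelated to selpercatinib, and no passage says to reverse the Yes/No answer.
- For known risks, the drug-side factors in Section 9.3 point towards selpercatinib.
- All SAEs through 28 days after the last dose are reported whatever their cause. The rule for later SAEs asks about study drug directly and does not cite Section 9.3.

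All of this stands. A reader might infer that drug-related AEs have in fact been undercounted, that the gaps above measure the undercount, or that the SAP's table cannot be produced. The documents support none of these. The gaps include events correctly judged unrelated, and the eCRF is not among the documents, so a direct drug-relatedness field may well exist.

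The reply does not remove the inconsistency. Section 9 and the SUSAR definition give no coding rule for an AE with two plausible causes. Section 8.5.2 sends the study-drug judgement to Section 9.3 and not to either of them. The published related percentages do not show which rule produced them.

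**Conclusion.** The point holds as an inconsistency with a possible direction of bias. Protocol Sections 9.3 and 8.5.2 define and tabulate relatedness by other causes, and SAP Section 4.3.11.2 does so by study drug. There is no mapping, no rule for dual-cause AEs and no entry in SAP Section 4.7. A table built as Section 8.5.2 lists it would not measure the relatedness endpoint in Section 8.1.

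An AE that fits both causes can be coded away from selpercatinib, so drug-related AEs can be undercounted. That they have been is not shown. For the five AEs with figures, the undercount lies between zero and 4.4 to 12.8 percentage points, depending on the AE. This rests on the Section 1.7.1 percentages as coded at the May 2022 cut-off; the patient counts also assume 825 as the denominator. For other AEs the documents give no bound. All-cause AE and SAE tables, and SAE reporting through 28 days, are unaffected.

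**What to change.** 1. Reword Section 9.3 so that the investigator records, for every AE, related or not related to selpercatinib, with reasonable possibility as the standard. The SUSAR definition already uses it.
2. State that an AE also compatible with another cause is still related when selpercatinib is a reasonable possibility.
3. Keep alternative cause as a separate field.
4. Change the two relatedness bullets in Section 8.5.2 to relationship to study drug, matching SAP Section 4.3.11.2.
5. For data already collected: if both answers exist, cross-tabulate them in the study report, so that readers can see how many events with a possible alternative cause were called related. If only the Section 9.3 answer exists, state how related was derived from it.

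The cost is protocol wording, eCRF completion guidance and one extra table or explanatory paragraph in the study report. If the eCRF already captures relationship to selpercatinib, only the wording and the table are needed. The downside is that reported drug-related rates may rise, and events coded before and after the change may not be fully comparable.
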